5.3 Risk-Benefit Assessment

All excipients in Lumentin® 44, expect EWP, are of pharmacopoeia quality (buffer and stabilizer) or belongs to a product range (flavor) registered under a Drug Master File (DMF) in the US, and widely used in pharmaceuticals. The EWP is widely used as a food ingredient.

The side effects reported in the pilot trial, by volunteers drinking up to 1.4 L of the preliminary formulation (containing 60% air) were mild and hence it is considered that L60 were well tolerated. Most common side effects observed were eructation, abdominal distension, and mild nausea.

Allergic reactions towards egg protein cannot be excluded and patients with a known sensitivity towards egg should not be exposed to Lumentin® 44.

Ingestion of a large volume of foam in a short time may have an effect on the resorption pattern of concomitant medications. Intake of other medications, which are absorbed in

the small bowel, and having a narrow therapeutic window, should be avoided within a period of four hours before and until one hour after administration of Lumentin® 44. The patients in the planned trial are all referred for routine abdominal CT examination. No direct benefit is expected for patients receiving Lumentin® 44 in this trial compared to those receiving Omnipaque® or Movprep®.

6 TRIAL OBJECTIVES

6.1 Primary Objective

To compare the mean difference in contrast density shown on abdominal CT-images when using the contrast agent Lumentin® 44, with abdominal CT-images using diluted Omnipaque® and with abdominal CT-images using Movprep®

6.2 Secondary Objectives

- To describe and compare the ability of Lumentin® 44 to fill the bowel as compared to Movprep® and diluted Omnipaque®.
- To describe and assess how Lumentin® 44 influences reading of the abdominal CT-examination as compared to Movprep® and diluted Omnipaque® with respect to:
 - Diagnostics with particular regard to parenchymal organs, lymphatic system and tissue compartments beyond the gastrointestinal tract
- To investigate signs of degradation of Lumentin® 44 in terms of
 - Coalescence
 - Syneresis or drainage
- Describe and compare the ability to eat/drink for each of three contrast agents with respect to:
 - Taste
 - Smell
 - Consistency
 - Ability to swallow
 - Fullness
- Validity and repeatability of the primary endpoint
- To evaluate safety and tolerability after oral administration of each of three contrast agents

7 OVERALL DESIGN AND PLAN OF THE TRIAL

7.1 Overview

An open, randomized, controlled, single centre phase 2 trial.

Blinding of the trial is not possible due to the clear differences in the features and properties of the contrast agents. Thus, subjects will be able to identify the contrast agent through taste and consistency and the investigators will be able to identify which contrast agent the subject has been given through its unique image grey-scale

Subjects referred for abdominal or thoracoabdominal CT-examination will be invited by letter to participate in the study. This invitation is added to the referral letter that informs them on day and time for the CT-examination. Referral letters are routinely sent out within 4 weeks prior to the examination. All subjects who has received an invitation letter will be contacted by phone by a study nurse. Those subjects who are interested in participating will be forwarded a full subject information about the trial and they will be asked to read it prior to the CT-examination visit.

Patients at the oncology departments at the hospital of Lund and Malmö will also be informed about the trial. Posters will be placed at the departments and invitation letters will be handed out to those interested.

Subjects still interested in participating in the trial will, upon arrival to the clinic at the day of CT examination, be fully informed about the trial by the investigator and given opportunity to ask questions. Eligible subjects will sign the consent to participate form prior to randomisation and any treatment related procedures.

Subject demography, medical history and concomitant medication will be recorded, and a clinical chemistry blood sample (2 mL) will be taken just prior to drinking the oral contrast agent.

Lumentin® 44 is given in volumes of 750 mL to 1 200 mL and Omnipaque® and Movprep® is given according to the general praxis of care at the department "Verksamhetsområde Bild och funktion Skånes Universitetssjukhus". At least 750 mL of Lumentin® 44 must be drunk. At least the recommended, according to the general praxis of care, volume of Omnipaque® and Movprep® must be drunk.

The subjects will be asked to drink the solutions of oral contrast agents within one hour. Subjects not able to drink at least 750 mL of Lumentin® 44 or, at least the recommended dose of Omnipaque® and Movprep®; will be classified as major protocol violators and the subject will be excluded from all efficacy evaluations.

During the time the subjects drink the contrast agent, the subjects will be asked to complete a questionnaire assessing taste, smell, consistency, fullness and ability to swallow the contrast agent.

The CT-examination will be started within 10 minutes after the contrast agent has been drunk and the CT-examination lasts in average eight minutes.

The CT-equipment comes with a moving table and a fixed gantry in which the X-ray tube is rotating with 2 revs per sec. The subject will be placed in supine on the table with hands-over-head, and prone for dedicated examination of the bowels. The table is then moved into the gantry for exposure of the abdomen. Before the examinations starts, an intravenous injection of an iodine based contrast medium (Omnipaque® 350 mg I/mL) is given in order to enhance any existing lesion or disease. The dose is adjusted to body weight and kidney function and is usually given in the range of 60 to 115 mL of Omnipaque® 350 mg I/mL. The dose and batch number of iodine will be noted in the eCRF.

At contrast peak in the aorta, and an extra fixed delay of 50 seconds, altogether approximately one minute, exposure starts and the table moves ahead while the body part is continuously irradiated from the rotating X-ray tube. The whole procedure is finished within 10 seconds and images presented within 30 seconds. After a quality check of the

CT-examination and affirmation of the subject's well-being, the subject is free to leave the CT-scanner.

The subject shall remain at the clinic for at least 30 minutes post the intravenous injection of the iodine based contrast medium in case of the occurrence of sensitivity reaction.

A post- examination clinical chemistry blood sample (2 mL) will be taken prior to the subject will be leaving the clinic and occurrence of any adverse events will be recorded.

The subjects will thereafter be free to leave the clinic.

For safety reasons, subjects will be contacted, within 12 to 48 hours after the examination by the investigator and asked about occurrence of any adverse event. No other follow-up is planned.

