Subjects in a previous explorative trial [1] were given 0.9 -1.5 L foam to take orally and 23 out of the 25 subjects could consume more than 0.9 L of the foam. The small bowel filling properties of the foam was on par with the normally used contrast agents, diluted Omnipaque® and Movprep®. A dose of 1 000 ml \pm 200 ml was therefore selected. Both route and treatment duration are according to standard praxis.

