13.1.2 Protocol Deviations

Deviations to the trial protocol will be documented in a Protocol Deviation Log.

Deviations from the protocol including violations of inclusion/exclusion criteria will be assessed as “minor” or “major” on a case-by-case basis in cooperation with the Sponsor. This assessment will take place during a data review meeting. Major deviations from the protocol will lead to the exclusion of a subject from the per protocol analysis set.

Unless decided otherwise during the data review meeting, the following will be major protocol deviations:

- Deviations of inclusion/exclusion criteria,
- Subjects not able to drink at least 750 mL Lumentin® 44
- Subjects not able to drink at least the, according to the general praxis of care, recommended dose of diluted Omnipaque®
- Subjects not able to drink at least the, according to the general praxis of care, recommended dose of Movprep®

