13.1.3 Analysis Populations

Safety set:	All subjects who received at least some portion of the contrast agents (Lumentin® 44, diluted Omnipaque® and Movprep®). Subjects will be included in the analysis according to the treatment actually received.
Full analysis (FA) set:	All correctly included and randomised subjects who received at least some portion of the contrast agents (Lumentin® 44, diluted Omnipaque® and Movprep®) and for whom a CT-scan has been performed. All subjects will be included in the group according to the intention based on the randomisation.
Per protocol (PP) set:	All subjects of the FA set who are compliant with the trial protocol, i.e., who do not experience any major protocol deviations.

All efficacy analyses will be performed for both the FA set and the PP set. The analysis of the primary efficacy parameter based on the PP set will be regarded as the primary analysis. The analyses on the FA set will be considered as sensitivity analyses.

All safety analyses will be based upon the Safety Set.

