13.4 Efficacy Analyses

The primary efficacy objective will be analysed using data from patients in both the FA set and the PP set considering the results from the PP set as the primary results.

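### Section 7.1 drops subjects below the minimum volume from all efficacy evaluations, while 13.1.2 and 13.1.3 drop them from the PP set only; following 7.1 would remove from FA the subjects needed to check the PP results

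*Combined protocol and SAP*

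**What the plan says.** Section 7.1 deals with subjects who drink less than 750 mL of Lumentin 44, or less than the recommended amount of a comparator. They "will be classified as major protocol violators and the subject will be excluded from all efficacy evaluations". The matching design text in the synopsis does not contain this sentence.

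Section 13.1.2 lists the same shortfalls as default major deviations but gives them a narrower consequence: "Major deviations from the protocol will lead to the exclusion of a subject from the per protocol analysis set". The list is open to revision: "Unless decided otherwise during the data review meeting, the following will be major protocol deviations".

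Section 13.1.3 defines FA as "All correctly included and randomised subjects who received at least some portion of the contrast agents" and who had a CT scan, with no minimum volume. PP is the part of FA without major deviations. It continues: "All efficacy analyses will be performed for both the FA set and the PP set", and "The analyses on the FA set will be considered as sensitivity analyses". Section 13.4 confirms the order, "considering the results from the PP set as the primary results", and 13.4.2 applies the same principles to the secondary objectives.

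Section 8.3 makes a volume shortfall a mandatory reason for withdrawal, refers to the early-termination evaluations in section 12, and adds that the clinic normally still performs the scan.

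**The concern.** A subject who drinks too little but is scanned belongs in FA under 13.1.3 and in no efficacy analysis under 7.1. No rule says which section governs, and section 13 says only that a separate SAP may be finalised, so a later document is not certain to settle it.

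PP is selected after randomisation on whether the subject could drink the assigned agent. The three agents differ in taste and consistency, so the proportion removed may differ by arm. FA is the plan's only check on whether the efficacy results depend on that selection. Disposition, withdrawal reasons, exposure and the Safety set would show that some subjects could not drink an agent. They would not show what leaving those subjects out does to the efficacy comparisons. For outcomes such as ability to swallow, fullness and bowel filling, the omitted subjects are among the most informative.

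**Working it through.** **Nearest figure in the plan.** The plan gives no figure on this point. The closest is the 78% power per comparison in 13.6.1 (difference 1.50, SD 2.00, 40 versus 20). Standard error = 2.00 × √(1/40 + 1/20) = 0.548; 1.50/0.548 = 2.739; 2.739 − 1.960 = 0.779; Φ(0.779) = 0.782. It reproduces. It is stated for evaluable subjects and does not depend on which rule is followed.

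**1. One subject under each rule.** Take an eligible, randomised subject who drinks some agent but less than the minimum, is scanned and does not withdraw consent.

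| | 7.1 | 13.1.2 and 13.1.3 |
|---|---|---|
| Major deviation | yes | yes, unless the data review meeting decides otherwise |
| In PP | no | no, by default |
| In FA efficacy analyses | no | yes |

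The last row is a direct contradiction. Section 8.3 makes the case foreseeable, because the scan is normally still done.

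**2. What would be left of the FA check under 7.1.** The default major deviations are eligibility violations and volume shortfall (written once per agent). Under 7.1, volume shortfall no longer separates FA from PP. Deviations judged major case by case still could. So could eligibility violations, depending on how the undefined condition of correct inclusion in the FA definition is read.

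**3. Which results are exposed.**
- Primary mean (10.1.1): segments the agent did not reach are left out of the mean, so a shortfall affects it less.
- Extension and distension (10.1.2): a segment without agent is graded 1 and counted. One segment graded 1 instead of 9 by both readers costs at most 2 × (9 − 1) = 16 points on a scale with range 90 − 10 = 80.
- Drinkability (7.2.2): ability to swallow and fullness are secondary efficacy variables.

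**4. Whether FA would have the data.** The early-termination column of Table 4 marks only concomitant treatment and adverse events. Section 8.3 mentions the scan as clinic practice and does not say that it is read for the trial. Appendix 2 asks subjects to rate drinkability and fullness only when they are about to go to the scan, so a subject withdrawn while drinking may have neither rating. Section 13.2 analyses observed cases without substitution. Correcting 7.1 alone could therefore leave FA with no efficacy data on these subjects.

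**5. How many.** The only intake figure is from the pilot (7.3.2): "23 out of the 25 subjects could consume more than 0.9 L of the foam". So 25 − 23 = 2 drank 0.9 L or less, and between 0 and 2 (0% to 8%) drank less than 0.75 L. Those were healthy volunteers given the 60% air formulation (5.2). No intake figure is given for the comparators.

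The Lumentin arm size is itself uncertain: 40:20:20 in the synopsis and 8.4, but 1:1:1 in 8.5. With 88 randomised:
- 40:20:20: 88 × 40/80 = 44; 0.08 × 44 = 3.5
- 1:1:1: 88/3 = 29.3; 0.08 × 29.3 = 2.3

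That is 0 to about 4 subjects if the pilot rate carries over. The exact 95% upper limit for 2/25 is 26.03%, which would give 11.5 or 7.6, but this adds sampling error to a count that is already a worst case.

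**6. Scale arithmetic, not an estimate.** With 8% under-drinkers, the Lumentin FA mean for extension or distension would differ from the PP mean by at most 0.08 × 16 = 1.3 points per unreached segment.

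**The case against.** The strongest reply is that section 13 plainly governs. It is the statistical section, it is consistent across 13.1.2, 13.1.3 and 13.4, and the conflicting text is one sentence in an overview that the synopsis omits. Most statisticians would follow section 13. This stands as a prediction, but nothing in the protocol gives section 13 precedence, and 14.2 requires strict adherence to the protocol as a whole.

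It can also be said that the effect is small: few subjects, and at most 1.3 of 80 points per unreached segment at the pilot's worst rate. This largely stands. The pilot rate may not carry over to referred patients, but no other rate is available. The 1.3 is also a shift in means, while the planned test is a Wilcoxon rank sum test, so it says nothing direct about a p-value.

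Three stronger readings are tempting, and the documents do not support them.
- A reader might infer that the primary result is at risk. PP is primary and excludes these subjects by default under both rules. The rules differ for PP only if the data review meeting downgrades a shortfall to minor.
- A reader might infer that FA would become identical to PP. The other deviations in step 2 can still separate them.
- A reader might take the Visit 1 column of Table 4 to mean that withdrawn subjects' scans are read for the trial. The early-termination column points the other way, and only the FA definition implies, indirectly, that efficacy data are expected.

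**Conclusion.** The contradiction is certain: the 7.1 sentence cannot hold together with 13.1.2 and 13.1.3. If 7.1 is followed, the FA sensitivity analyses lose the subjects who fell short on volume and no longer test whether the results depend on selection by ability to drink. The consequence is confined, by default, to the FA analyses. It is greatest for extension, distension and the drinkability ratings, and weaker for the primary mean.

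The size of any bias cannot be derived. The number of subjects is probably small (0 to about 4 in the Lumentin arm, assuming the pilot rate applies and 88 are randomised), and the documents give no basis for the comparator arms. The gap over readings after withdrawal in 8.3 and Table 4 belongs to the same point, because it decides whether FA has anything to analyse. Severity: minor to should-fix.

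**What to change.** 1. In 7.1, replace exclusion from all efficacy evaluations with exclusion from the PP set only, in line with 13.1.2 and 13.1.3.
2. Reconcile 8.3 and the early-termination column of Table 4 with the FA definition in 13.1.3. State that, where a scan is performed and consent is not withdrawn, both readers' assessments and any questionnaire ratings obtained are recorded and analysed in FA by randomised arm.

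The volume minimum, the withdrawal trigger and PP as the primary set stay as they are.

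The cost is wording plus a little extra work for the two existing readers on scans the clinic normally does anyway. Per affected subject this is at most 18 ROI values (9 × 2), 10 extension grades (5 × 2), 10 distension grades (5 × 2), 6 diagnostic-ability grades (3 × 2) and 20 degradation items (5 × 2 × 2), or 64 in all; four subjects would mean 4 × 64 = 256. No patients or visits are added.

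Two further steps are separate and optional: stating that the data review meeting settles major or minor status before it sees efficacy results by arm, and adding a disposition row for subjects in FA but not PP. Counts for that row can largely be derived from the FA and PP tables already planned in 13.3.

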7.2 Parameters

7.2.1 Primary Efficacy Variable

The mean difference in contrast density in HU, expressed as the mean of 11 measurements of contrast density differences between bowel lumen and wall (mucosal lining) performed in the selected 5 sub-segments of the small bowel.

7.2.2 Secondary Efficacy Variables

- Bowel filling properties (extension and distension) on Abd-CT in each of 5 selected sub-segments of the small bowel
- Degradation (presence of bubbles and signs of sedimentation) on Abd-CT in each of 5 sub-segments of the small bowel
- Diagnostic ability on Abd-CT of the parenchyma, lymphatic system and tissue compartments beyond the gastrointestinal tract.
- Subject assessments of taste, smell, consistency, ability to swallow and fullness after swallowing the contrast agent

7.2.3 Safety Variables

The safety parameters consist of:

- Especially solicited adverse events (AEs), i.e. stomach ache, burping, letting go of wind, Nausea and sensation of fullness
- Any treatment emerging adverse events
- Any treatment emerging adverse drug reactions (ADR)
- Safety laboratory evaluations (clinical chemistry)
- The reasons for withdrawal from the trial

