An intensified small bowel wall is currently depicted on images acquired with magnetic resonance imaging, MRI, technique [2]. On a special MRI-sequence the small bowel lumen appears dark. After IV. gadolinium contrast administration, the small bowel wall with its mucosa stand out with increased signal intensity (bright), particularly in a case with inflammatory bowel disease. The induced contrast enhancement facilitates and improves diagnostics. Unfortunately, the availability of MRI equipment is limited compared to that of CT, and is therefore mostly reserved for young subjects with inflammatory bowel disease, for those who need repeated imaging, and for those with complicated diseases of the small bowel. Thus, most subjects with abdominal problems needing imaging are referred for abdominal-CT (Abd-CT). It would therefore be desirable to present CT-images with a dark small bowel lumen, as seen on certain MRI sequences. In order to allow for the odd and clinically silent small bowel lesion to be unveiled, a “black” bowel lumen would be advantageous in all subjects for Abd-CT. Scientists have been eager to pursue this idea since the 1980s. Furthermore, radiologists have for decades expressed a wish for a negative bowel contrast in order to improve diagnostics and tested several agents based on fat and bubbles. So far none has been clinically successful [3-12] while a number of side-effects were reported in association with oil-based contrasts such as abdominal cramps, diarrhoea and oily taste. Furthermore, many of these bowel filling agents have been denominated as being negative although they were assigned higher mean scores than water in each segment of the bowel, i.e. with positive HU. Still, the use of a neutral oral contrasts, with HU of around that of water, have been established in clinical routine due to improved CT-diagnostics.

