10.3 Reporting of Adverse Events

All trial subjects will be carefully monitored for the occurrence of AEs during the trial period, from start of intake of the first dose until the contact 2, telephone interview 12 – 48 hours after the CT-examination. Reported AEs will be followed up (see 10.4 below). The Investigator will collect AEs with a non-leading question such as “have you experienced any new health problems or worsening of existing conditions” as well as reporting events directly observed or spontaneously volunteered by subjects.

Clearly related signs, symptoms and abnormal diagnostic procedure results should be grouped together and reported as a single diagnosis or syndrome whenever possible.

All AEs including but not limited to events reported by the subject, or reported in answer to an open question by the Investigator or member of this team, which fall into any of the above definitions must be recorded as an AE in the eCRF and should include the following information:

- Brief description of the event (diagnosis)
- Start date (and time, if relevant)
- Stop date (and time, if relevant) (or resolution)
- Severity
- Action taken regarding trial treatment
- Opinion on causality

- Seriousness
- Outcome

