12.1.3 Contact 2, Telephone interview

The subject will be contacted by telephone by the investigator 12 to 48 hours after the CT-scan visit and interviewed about any possible adverse events that has occurred during the period after the CT-scan. The interview will include a set of predefined questions (see appendix XX) and also an open question, e.g. “have you experienced any untoward events or side effects since you left the clinic”. Concomitant medication and any change in concomitant medication will also be checked.

During telephone interview, the Investigator will:

- Check any occurrence or change in adverse events
- Check of use or change in concomitant medication

SAE and other AEs that the investigator assesses as relevant to follow from a trial perspective will be followed up, see section 10.4

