Tack på förhand för att ni hjälper oss med att utvärdera kontrastdrycken!

Kontrastdryckens egenskaper:

	Mycket-negativ	Negativ	Neutral	Positiv	Mycket-positiv
Smak					
Lukt					
Konsistens					
	Mycket-svårt	Svårt	Medium	Lätt	Mycket-lätt
Drickbarhet					
	Mycket-mätta	Mätta	Lagom-mätta	Omätta	Mycket-omätta
Mättnadskänsla					

Ifyller av studiepersonal

Patientnummer:

Patient-Id:

Datum: År Månad Dag Studiesjuk-Signatur:

Appendix 3

Protocol: LUM-001, Version: 1.0

→

Rapporteringsformulär inför uppföljningssamtal 12-48 timmar efter CT-undersökning

Patientnummer:

Patient Id:

Vid uppföljningssamtalet följes nedan angivna beskrivning. Det är av vikt att alla patienter utfrågas på ett likvärdigt sätt för att få en så objektiv bedömning av eventuella biverkningar och användande av läkemedel.

Börja intervjun med att fråga om patienten tagit några läkemedel sedan sist eller ändrat sin dosering av redan rapporterad pågående läkemedelsbehandling. För pågående läkemedelsbehandling, var god se patientens journal.

Använd en öppen fråga, t.ex: har ni tagit något läkemedel sedan ni lämnade kliniken efter er CT-undersökning eller ändrat eller slutat ta eventuell behandling ni har haft?.

⊕

Har patienten tagit något nytt läkemedel eller ändrat pågående medicinering?

Jas	Nej
	

Om patienten har tagit nytt läkemedel eller ändrat sin medicinering fylls patientjournalens "concomitant medication form" i.

Fråga därefter ut patienten om eventuella biverkningar. Använd en öppen fråga, t.ex: har ni haft några besvär eller obehag sedan ni lämnat kliniken efter er CT-undersökning?.

Har patienten rapporterat någon biverkan?

Jas	Nej
	

Om patienten svarar ja på denna fråga så fylls patientjournalens "AE form" i. Använd en AE form för varje enskild biverkan.

..... Sidbrytning

Protocol: LUM-001, Version: 1.0 →

¶

Om patienten har rapporterat någon biverkning under tiden på kliniken och denna fortfarande var pågående när patienten lämnade kliniken, så frågas patienten ut om det skett några förändringar. ¶

¶

Har patienten rapporterat förändring på pågående biverkan? ☐

Jaa	Nej
☐	☐

Notera eventuella förändringar i patientjournalens "AE form". Använd en AE form för varje enskild biverkan. ¶

¶

¶

Därefter frågas patienten ut om han/hon haft problem med: ¶

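### The solicited adverse-event list prompts two of the three most common side effects of the pilot foam, but not the third, abdominal distension

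*Combined protocol and SAP*

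**What the plan says.** The safety variables in section 7.2.3, repeated in the synopsis, open with a list of five named symptoms: "Especially solicited adverse events (AEs), i.e. stomach ache, burping, letting go of wind, Nausea and sensation of fullness". The next item is broader: "Any treatment emerging adverse events".

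The Appendix 3 telephone form puts the same five to the subject in Swedish (Magknip, Mättnad, Rapningar, Vädersläpp, Illamående), introduced by "Därefter frågas patienten ut om han/hon haft problem med". Section 12.1.3 describes that contact: "The interview will include a set of predefined questions (see appendix XX) and also an open question". The appendix number there was left as a placeholder, but Appendix 3 is evidently the form meant.

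Section 5.3 summarises tolerability of the 60% air formulation: "Most common side effects observed were eructation, abdominal distension, and mild nausea".

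Outside the checklist, section 10.3 states: "The Investigator will collect AEs with a non-leading question such as", followed by an example, and it also requires observed and volunteered events to be recorded. Section 13.4.5 plans an overall summary table with Fisher's exact test for the three pairwise arm comparisons, and shows the number of reported events in the same table. It defines no separate table or test for the solicited symptoms.

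**The concern.** A symptom that is asked about by name tends to be reported more readily than one the subject has to volunteer. A list that prompts some known effects of a product and leaves out another can therefore tilt the recorded profile towards the prompted ones. Here the omitted symptom is one the protocol itself places among the three most common for this type of foam, and no reason is given for leaving it off.

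Safety and tolerability of each agent is a stated secondary objective (section 6.2), and Appendix 3 stresses that all patients be questioned in an equivalent way. If distension is in fact more frequent with the foam than with the comparators, weaker capture would flatter the investigational product. The gap cannot be filled once the interviews, 12 to 48 hours after the CT examination, have been held.

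**Working it through.** The check compares texts; there is no stated figure to reproduce.

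**Step 1: match the pilot effects to the solicited items.**

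| Pilot effect (5.3) | Synopsis and 7.2.3 | Appendix 3 |
|---|---|---|
| Eructation | burping | Rapningar |
| Mild nausea | nausea | Illamående |
| Abdominal distension | none; nearest is sensation of fullness | none; nearest is Mättnad |

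Two of three are prompted by name. The other two solicited items, stomach ache (Magknip) and wind (Vädersläpp), are different symptoms.

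**Step 2: does fullness cover distension?** Section 10.1.5 has subjects rate fullness from very full to not at all full, alongside taste, smell, consistency and ability to swallow. The Appendix 2 form calls this item Mättnadskänsla and runs it from very sated to very unsated. In that use the word means satiety. Section 5.3, by contrast, treats abdominal distension as a side effect in its own right. A subject asked about Mättnad has not clearly been asked about a swollen or bloated abdomen.

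**Step 3: where else could distension be recorded?** Through the non-leading question and direct observation (10.3), and through the open telephone question (12.1.3). In Appendix 3 that open question asks about any trouble or discomfort and comes before the checklist. Distension can therefore be recorded, but without the prompt that burping and nausea receive.

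**Step 4: which outputs would change?**
- *Number of reported events and symptom profile:* each unreported distension event is missing from both.
- *Any-TEAE row:* a subject's status changes only if distension is that subject's sole treatment-emergent event and it goes unreported. A subject who also reports burping, nausea, wind, stomach ache or fullness already counts as affected.
- *Severe or drug-related rows:* the same logic applies when distension is the only event in that category.

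With the planned 40, 20 and 20 evaluable subjects, each such subject moves a row by 1/40 = 2.5 percentage points in the Lumentin arm and by 1/20 = 5 points in a comparator arm. The safety set may be somewhat larger, which would make these steps smaller.

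**Step 5: can the total effect be sized?** Recorded frequency = true frequency × fraction captured. The documents give neither factor: section 5.3 states no pilot rates, and nothing is said about how much an open question captures. No total follows.

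**The case against.** The strongest reply is that distension is not left uncollected. All treatment-emergent events are a safety variable, open questions are asked at the clinic and by telephone, and on the telephone form Mättnad is asked as a problem, not as a drinkability rating, so some subjects with bloating will say yes to it. The pilot is also indirect evidence: healthy volunteers took up to 1.4 L of a 60% air foam with only mild effects, whereas this trial gives a 44% air product to referred patients. All of this stands. It is why the conclusion is that distension may be under-recorded, not that it will be. It does not explain why the other two leading pilot effects are prompted and this one is not. Nor does the distension score in section 10.1.2 fill the gap: it grades bowel-loop filling on the CT images, not a symptom.

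Four stronger readings are tempting and are not supported:

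- *That diarrhoea is likewise an expected effect missing from the list.* Section 5.1 mentions it once, for "oil-based contrasts such as abdominal cramps, diarrhoea and oily taste". The documents do not report it for the foam or for either comparator.
- *That the arm comparison of tolerability rests on the checklist and is distorted.* The Fisher tests use overall rows that include unsolicited events, and no symptom-level test is planned.
- *That a percentage loss can be quoted.* Any such figure would rest wholly on assumed rates.
- *That the single yes/no box for all five symptoms prevents symptom-level counts.* Appendix 3 already requires a separate AE form for each side effect.

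**Conclusion.** The point holds as a modest, inexpensive improvement. The solicited list and the telephone checklist omit one of the three side effects that section 5.3 calls most common, and the fullness item does not clearly stand in for it. Distension may be under-recorded relative to burping and nausea. The event counts and symptom profile are exposed directly; the rows tested by Fisher's exact test are exposed only through subjects whose sole, or sole severe or drug-related, complaint is distension.

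The size is unknown and cannot be derived from the documents. The conclusion rests on two assumptions: that prompting raises reporting, and that the 60% air pilot says something about the 44% air product. The primary endpoint is not affected.

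**What to change.** Add abdominal distension/bloating as an item separate from fullness in three places: the synopsis safety variables, section 7.2.3 and the Appendix 3 checklist. Use a Swedish term on the form that cannot be read as satiety, and ask it identically in all three arms. A yes/no box per symptom would also record explicit negative answers, but it is optional.

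The cost is one extra line on a short telephone form, with matching eCRF wording if needed. Reported event percentages may rise slightly in every arm.
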